### **9.3.2 Implementation**

All HCPs:

- Reception of the education materials (brochure and maybe Patient Card depending on the type of HCPs).

### **9.3.3 Knowledge of each safety messages**

Key safety message for All HCPs:

- Isatuximab is associated with risk of interference with blood compatibility tests

Prescribers:

- There is currently no available information on how long the interference may persist after the last infusion of isatuximab. Based on the half-life of isatuximab, the interference with indirect antiglobulin tests may persist for approximately six months after the last infusion.

Non-prescribers:

- Isatuximab bound to CD38 on RBCs and may mask the detection of antibodies to minor antigens in the patient's serum. Isatuximab may interfere with routine blood compatibility tests with potential false positive reactions in IAT.
- The determination of a patient's ABO and Rh blood type are not impacted

### **9.3.4 Behaviour with respect to the safety messages**

Prescribers:

- All patients should be blood typed and screened prior to start treatment with isatuximab.

- 
- Consider phenotyping prior to starting isatuximab treatment as per local practice.
  - If treatment with isatuximab has already started, inform the blood bank that the patient is receiving isatuximab.
  - In the event of a planned transfusion, notify blood transfusion centres about the risk of interference with indirect antiglobulin tests.
  - Verify standing orders for transfusions to determine if your patient received isatuximab within the last year.
  - Give the Patient Card to the patients and advise them to carry it at all time and until six months after the last dose of isatuximab. Provide patient's pre-isatuximab compatibility profile, if available, to the blood bank.
  - Ask your patient to tell their other healthcare professionals that they have received isatuximab, particularly before a transfusion, and to show them their Patient Card.

Non-prescribers:

- In case of urgent need for transfusion, non-cross matched ABO/RhD compatible RBC units can be administered as per local bank practices.
- The interference mitigation methods include treating reagent RBCs with DTT to disrupt isatuximab binding or other locally validated methods.
- Since the Kell Blood group system is also sensitive to DTT treatment, Kell-negative units should be supplied after ruling out or identifying alloantibodies using DTT-treated RBCs.

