## WARNING FOR HEALTHCARE PROFESSIONALS

### APPROPRIATE MEASURES TO MANAGE ISATUXIMAB INTERFERENCE AND AVOID POSSIBLE RESULTING ADVERSE CLINICAL CONSEQUENCES

- Conduct blood type and screen tests on your patient prior to the first infusion of isatuximab.
- Consider phenotyping prior to starting isatuximab treatment as per local practice.
- Give your patient the latest version of the **Patient Card**.
- If treatment with isatuximab has already started, inform the blood bank that the patient is receiving isatuximab.
- In the event of a planned transfusion, please notify blood transfusion centers about the risk of interference with indirect antiglobulin tests.
- There is currently no available information with regards to how long the interference with the indirect Coombs test may persist after the last infusion of isatuximab. Based on the half-life of isatuximab, it is anticipated that isatuximab mediated positive indirect Coombs test may persist for approximately **6 months** after the last infusion. Therefore, please advise your patient to carry the Patient Card at all times and until 6 months after the last dose of isatuximab.
- It is important you always advise your patient to consult the Package Leaflet (PL) for further information on isatuximab.

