## FOR TIMELY TRANSFUSIONS

### REMINDER FOR HEALTHCARE PROFESSIONALS

- Conduct blood type and screen tests on your patient prior to the first infusion of isatuximab. Inform the blood bank that your patient has been treated with isatuximab which may interfere with indirect antiglobulin tests (indirect coombs tests).

- Verify standing orders for transfusions to determine if your patient received isatuximab within the last year.

- In the event of a planned transfusion, notify blood transfusion centers about the risk of interference with indirect antiglobulin tests.

- Give your patient a Patient Card to be carried at all times and until **6 months** after the last dose of isatuximab. Provide your patient's pre-isatuximab compatibility profile, if available, to the blood bank.

- Ask your patient to tell their other healthcare professionals that they have received isatuximab, particularly before a transfusion, and to show them their Patient Card.

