### REMINDER FOR BLOOD BANKS

- Identify the blood sample of your patient as containing isatuximab.

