**9 Which of the following is correct regarding the Patient Card:**

- A. Give the Patient Card to the patients and advise them to carry it until the last dose of isatuximab.
- B. Give the Patient Card to the patients and advise them to carry it at all time and until six months after the last dose of isatuximab.
- C. Blood test results on the Patient Card are only from after starting isatuximab treatment.

[Correct answer: B]

PI- List drop down

[DP:1]

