**Behavior questions: Q5-Q7**

- 5 Select true or false for the following statement: *“In case the patient has urgent need for transfusion, Non-cross matched ABO/RhD compatible RBC units cannot be administered.”*
- True
  - False

[Correct answer: False]

PI- List drop down

[DP:1]

- 6 The interference mitigation methods such as treating reagent RBCs with dithiothreitol (DTT) is mainly to:
- A. Disrupt isatuximab binding to CD38
  - B. Destroy isatuximab so that it does not bind to CD38
  - C. Oxidize CD38 receptor bonds to prevent antibody from binding
  - D. None of the above

[Correct answer: A]

PI- List drop down

[DP:1]

- 7 Select true or false for the following statement: *“Kell-negative units should be supplied after ruling out or identifying alloantibodies using DTT-treated RBCs, this is because Kell Blood group system is also sensitive to DTT treatment.”*
- True

- False

[Correct answer: True]

PI- List drop down

[DP:1]

-----Page Break-----  
-----

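### Two scored behaviour items do not match their messages in 9.3.4: prescriber Q9 omits the compatibility profile, and non-prescriber Q5 drops the local-practice condition

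*Protocol*

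**What the plan says.** Section 9.3.4 lists seven behaviour messages for prescribers and three for non-prescribers. Appendix C gives each one scored item: prescriber Q4 to Q10 and non-prescriber Q5 to Q7. Section 9.7.4 requires 80% of prescribers to be right on at least five of seven items and 80% of non-prescribers on at least two of three. Both are joined by AND to the key knowledge question.

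**Prescriber message 6.** After the Patient Card instruction, 9.3.4 adds: "Provide patient's pre-isatuximab compatibility profile, if available, to the blood bank". The brochure repeats it in its reminder for healthcare professionals: "Provide your patient's pre-isatuximab compatibility profile, if available, to the blood bank". The keyed option of Q9 is confined to the card: "Give the Patient Card to the patients and advise them to carry it at all time and until six months after the last dose of" (only the drug name is cut from the end of this quote).

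**Non-prescriber message 1.** Section 9.3.4 says that in urgent need "non-cross matched ABO/RhD compatible RBC units can be administered as per local bank practices". The blood-bank warning in the brochure carries the same local-practice condition. Non-prescriber Q5 says "Non-cross matched ABO/RhD compatible RBC units cannot be administered", with False as the correct answer and no third option. Section 9.4 gives don't-know and not-applicable answers as examples of the response format; Appendix C offers neither on this item.

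**The concern.** Criteria 2 and 3 stand for adherence to the listed messages, so each item should capture what its message asks.

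In Q9 half of the message is unscored. Knowledge of the profile step could be absent throughout the sample and no result would show it.

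In non-prescriber Q5 the message defers to local practice but the item does not. Someone whose local practice excludes such units has reason to answer True and is then counted as wrong. Criterion 3 rests on three items and, by Table 3, on 40 to 100 respondents. Because the criteria are joined by AND, missing criterion 3 alone fails the overall threshold.

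**Working it through.** **Step 1: map messages to items.** The plan states no figure on this point, so the first check is a comparison of texts.

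| Message in 9.3.4 | Item | What is scored |
|---|---|---|
| Prescriber 6, first part: Patient Card | Q9, option B | Giving the card and how long it is carried |
| Prescriber 6, second part: profile to blood bank | none | Nothing |
| Non-prescriber 1: urgent transfusion, subject to local practice | Q5 | A categorical negative, without the condition |

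The nearest Q9 distractor is "Blood test results on the Patient Card are only from after starting isatuximab treatment". It concerns when the results on the card were obtained, not passing a profile to the blood bank. Prescriber Q6 and Q7 concern telling the blood bank about treatment and about the interference risk. Neither mentions the profile.

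Prescriber Q5 shows that an item can keep its qualifier: it asks about phenotyping and retains the reference to local practice.

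**Step 2: possible effect on criterion 3.** Let p be the chance of a correct answer on each item. Assume p is equal across items and items are independent; p is assumed, because the documents give no value.

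- Unaffected respondent: P(at least 2 of 3) = 3p² − 2p³.
- Respondent marked wrong on Q5 because of a local rule: both other items must be right, so P = p².
- If a share f of non-prescribers is affected, the expected rate is (1 − f)(3p² − 2p³) + f·p².
- Setting this to 0.80 gives f = (3p² − 2p³ − 0.80) / (3p² − 2p³ − p²).

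| p | Unaffected | Affected | f at which the expected rate reaches 80% |
|---|---|---|---|
| 0.70 | 0.784 | 0.490 | already below 80% with nobody affected |
| 0.75 | 0.844 | 0.5625 | 0.0438 / 0.2813 = about 16% |
| 0.80 | 0.896 | 0.640 | 0.096 / 0.256 = 37.5% |
| 0.85 | 0.939 | 0.7225 | 0.139 / 0.217 = about 64% |
| 0.90 | 0.972 | 0.810 | never; the rate stays at or above 81% |

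**Step 3: effect on criterion 2.** No calculation is needed. The profile step contributes nothing to any prescriber's score, so the maximum of 7 of 7 is open to someone who has never heard of it.

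**The case against.** Section 9.4 announces that some items will be traps built on false statements. Set against a message that such units can be given under local practice, a flat statement that they cannot is false, so the key can be defended. That stands: the key does not contradict the message outright. What remains is an ambiguity for respondents under a restrictive local rule. The documents do not say whether such rules exist or how common they are.

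The hand-over to the blood bank is also largely covered by prescriber Q6 and Q7, and the profile action applies only where a profile is available. That limits the weight of the Q9 gap but does not close it, since 9.3.4 lists the action.

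A reader might infer three stronger points that the documents do not support.

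- *Criterion 3 would fail because 72% is below 80%.* At p = 0.85 the 72% is one affected respondent's chance of passing. The 80% bar is a proportion of all non-prescribers, so the two are not comparable.
- *The questionnaire as a whole misses its messages.* Prescriber Q4 to Q8 and Q10 and non-prescriber Q7 follow theirs closely.
- *Leaving out the brochure's blood-bank reminder, "Identify the blood sample of your patient as containing isatuximab", is an error.* Section 9.3 refers to actions listed in the materials but does not promise an item for every line, and 9.3.4, which makes the selection, does not list this one. The brochure's advice "It is important you always advise your patient to consult the Package Leaflet (PL) for further information on isatuximab" is likewise unlisted and unscored. Which lines to score is largely a design choice.

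**Conclusion.** The point holds for two items. That Q9 leaves the profile action unscored follows from the text and needs no assumption. That non-prescriber Q5 omits a condition carried by both of its sources is equally plain.

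The size of the Q5 effect is unknown. It depends on how many respondents work under a restrictive local rule and on the true p, and the table in the working also rests on independent items of equal difficulty. Within that model the verdict on criterion 3 could turn at modest shares if p is near 0.75, needs a majority affected at p = 0.85, and does not turn at p = 0.90.

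The texts should be reconciled; no view is taken on which transfusion practice is right. The change is worth making because the items feed the success criteria and cannot be repaired after data collection.

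**What to change.** Make the changes in Appendix C before the pilot interviews and translation validation described in 9.4.

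1. **Non-prescriber Q5.** Reconcile it with 9.3.4 and the brochure. One way is to use the source message's own positive wording with its local-practice qualifier and re-key the item. Do not insert the qualifier into the negated statement: that would give someone under a restrictive rule more reason to answer True and still score it wrong. Another way is to add the not-applicable option that 9.4 mentions, with a stated rule for how it counts towards two of three.
2. **Compatibility profile.** Add a prescriber item, or include the profile in the keyed option of Q9. The second keeps seven items but cannot show which half of the message was missed.
3. **Counts.** If a prescriber item is added, restate the pass count. The choice matters: under the same model at p = 0.80, five of seven gives 0.852 and six of eight gives 0.797.
4. **Non-prescriber Q6.** Keep it; it is the only direct item for the listed message on mitigation methods.
5. **Optional.** The sample-identification reminder may be added to 9.3.4 and Appendix C, with the non-prescriber count restated.

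The cost of the required changes is at most one extra item in a questionnaire of about 15 minutes, plus restated counts.

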### **9.3.5 Exposure**

Not Applicable

## **9.4 Data Sources**

This study will require primary data collection, as the most appropriate method of data collection for the study objectives is through questionnaires. The questionnaire will be short (approximately 15 minutes). A set of standard questions will be developed for each target group. Questions will be 1) concise and understandable; 2) close-ended (e.g. yes/no/I don't know/Not-Applicable to my setting answers or true/false/I don't know answers; 3) including some traps (e.g. some questions will present false statements). The HCPs will have the possibility to fill in the questionnaire either in English or in their native language. The questionnaire in English and its translations will be validated via pilot interviews with two HCPs in each country after a user acceptance testing phase.

Questions in questionnaire will not be revealed before the HCP opens it. Once the HCP has saved their answers, they will not be allowed to go back and change the answers. Both of these strategies are in an effort to reduce the possible Hawthorne effect.

The target populations will include HCPs involved in the management and follow-up of multiple myeloma, such as haematology/oncology specialists and HCPs associated with transfusion centres.

## 9.5 Study Size

The proportions of interest (p) here are the proportions of HCPs knowledgeable and adherent to the aRMMs. As the proportion of interest (p) is not known at the time of this document, we may consider it to be 50% (maximum uncertainty). Such a hypothesis yields the most conservative (largest) sample size. Based on a minimum level of precision of 5%, the minimum required sample size would be 384 for precision levels of 5% for the overall population. The sub-populations of interest will include prescribers (75% to 90%) and non-prescribers (10% to 25%) but the study is not powered for the analysis by sub-population.

Of note, similar aRMMs were distributed to HCPs in Europe after the market authorisation was granted to the first-in-class compound (daratumumab). Based on the information published in February 2021, a total of 408 participants completed the questionnaires.

In order to obtain 400 completed questionnaires in our study, it is estimated that approximately 6,000 to 9,000 HCPs will be approached. This is based on the details provided in [section 9.2.3](#).

## 9.6 Data Management

A data management plan will be prepared and will detail the data management and data handling procedures.

Data for this study will be collected electronically by Evidera, the owner of LiveTracker™ platform. LiveTracker™ is a cloud-based, real-time, continuous electronic data collection platform that delivers real-world evidence data. LiveTracker™ has the capability to perform automatic checks of data quality and missing-ness. The administration of measures will be conducted according to the protocol.

### 9.6.1 Data Collection

Data for this study will be collected electronically by Evidera, the owner of LiveTracker™ platform. LiveTracker™ is a cloud-based, real-time, continuous electronic data collection platform that delivers real-world evidence data. LiveTracker™ has the capability to perform automatic checks of data quality and missing-ness. The administration of measures will be conducted according to the protocol.

---

Once HCPs click on their unique online data collection form link, they will be tracked through a unique identifier within the LiveTracker™ platform. The HCP will be asked to complete the self-reported items. The questionnaire is assumed to take approximately 15 minutes to complete. Each HCP has ultimate responsibility for the self-reporting of all data entered in the LiveTracker™, and ensuring that they are accurate, complete, consistent, legible and timely (contemporaneous).

HCPs who delay in completing the survey or who do not complete all contents of the survey in a session will be encouraged to complete their forms through e-mail and/or phone reminders. Any queries to the HCPs will be monitored until resolution within the LiveTracker™ platform through the electronic query report. The survey is considered valid if all questions are completed.

A small amount of incentive payment (country-specific fair market value payments based on physician contracts through the LiveTracker™ Panel, as allowed per the local law and regulations) will be made to HCPs as a compensation for the time spent to complete the questionnaire (about 15 minutes).

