## 9.9 Limitations of the Research Methods

All data supplied will be self-reported by the HCP, and it will not be possible to objectively verify information. The number of HCPs included will vary among countries, so the precision of country-level subgroup analyses will vary. The study uses descriptive statistics only. Therefore, it is not possible to determine whether findings are statistically significant or could be due to chance. However, given that the main objectives are to describe implementation of the aRMMs and to assess knowledge and behaviours, descriptive statistics are sufficient.

The survey will be completed by HCP on a voluntary basis. Thus, there is always the possibility that HCP accepting to participate will have different characteristics and different behaviours than non-responders. In order to identify any such selection bias, the characteristics of responders and non-responders will be described. Detailed description on minimizing selection bias during recruitment can be found in Section 9.2.

In addition, in order to reduce information bias and the possible Hawthorne effect, questions will be close-ended to avoid errors in interpreting free-texts during assessment; questions in questionnaire will not be revealed before the HCP opens it; HCPs will not have the possibility to come back and change their answers once submitted and will not be contacted to clarify or revise their survey responses. The results will reflect the knowledge, understanding and

 Non-responder's characteristics available in the LiveTracker™ panel profile.

 Overall target population characteristics available in the LiveTracker™ panel profile.

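### Section 9.6.1 allows open-ended queries to respondents, against the safeguard in 9.9, and lets part-seen surveys be resumed without flagging them

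*Protocol*

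**What the plan says.** Section 9.6.1 (Data Collection) expects some healthcare professionals (HCPs) not to finish in one sitting. It provides that "HCPs who delay in completing the survey or who do not complete all contents of the survey in a session will be encouraged to complete", with prompts by e-mail or phone. The next sentence adds: "Any queries to the HCPs will be monitored until resolution within the LiveTracker™ platform through the electronic query report". The same section counts a survey as valid only when every question has been answered, and section 9.7.2 builds the primary analysis population from valid questionnaires.

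Section 9.9 (Limitations) describes how information bias and the Hawthorne effect are to be reduced. Questions stay hidden until the form is opened, "HCPs will not have the possibility to come back and change their answers once submitted", and HCPs "will not be contacted to clarify or revise their survey responses". Section 9.4 has a similar lock at a different moment: "Once the HCP has saved their answers, they will not be allowed to go back and change the answers".

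Section 9.4 also says that the questionnaire and its translations will be "validated via pilot interviews with two HCPs in each country", following user acceptance testing. The only exclusion criterion in section 9.2.2 is earlier enrolment in this study.

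**The concern.** The survey is meant to show what HCPs know and would do unaided. Its three success criteria (the key knowledge item, five of seven behaviour items for prescribers, two of three for non-prescribers) are each judged against 80%. Anything that turns wrong answers into right ones after the respondent has seen the item pushes all three towards success.

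Three features open such a route. First, queries are unrestricted in scope and are pursued until resolved. Second, an HCP may leave with items displayed but unanswered and be prompted to return. Third, the pilot participants will already have seen the items and are not clearly barred from the survey. The first also leaves the vendor with two instructions that cannot both be followed if a scored answer is ever queried. Scored answers cannot be collected again unaided, so these points need settling before data collection starts.

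**Working it through.** The check is mainly a comparison of passages. The protocol gives no figure for the bias.

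**1. Queries (9.6.1) against no contact (9.9).**
- 9.6.1 places no limit on the subject of a query. Section 9.6.2 adds validation and edit checks without exempting scored items.
- 9.9 rules out contact whose purpose is clarifying or revising a response.
- All scored items in Appendix C (prescribers Q2-Q10, non-prescribers Q2-Q7) are closed drop-downs with one correct option. A query on an answered item has two possible results: the answer stands or it changes. Either is contact of the kind 9.9 excludes.
- Result: the two sections conflict for scored items. They do not conflict for screening, practice-setting or technical queries.

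**2. Reminders (9.6.1) against no contact (9.9).**
- A reminder asks for items not yet answered. It neither clarifies nor revises an existing response.
- Result: no contradiction.

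**3. What resumption leaves open.**
- Concealment ends when the form is opened.
- The lock applies to saved answers in 9.4 but to submitted answers in 9.9. On the 9.4 wording, a page saved before a break is fixed. On the 9.9 wording alone, it is fixed only at final submission.
- Neither section says what happens to items displayed but not answered when the HCP exits.
- By the page breaks in Appendix C, prescribers see Q1 to Q4 on one page, including the key item (Q2) and the duration item (Q3).
- Table 1 lists website distribution of the materials in Switzerland, Sweden, the Netherlands, Poland and Germany. The first three are confirmed countries.
- Once complete, a resumed survey is valid and enters the primary population like any other.
- Result: there is a real gap, but it is confined to items seen and not yet saved.

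**4. Why completions are worth keeping.** The expected response rate in 9.2.3 reproduces: 0.17 × 0.26 = 0.044 and 0.17 × 0.40 = 0.068. So do the invitation numbers: 9,000 × 0.044 = 396 and 6,000 × 0.068 = 408, both close to 400. Table 3 plans only 40 to 100 non-prescribers. A rule that discards break-offs would draw on a small supply.

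**5. Pilot participants.**
- Two per country in at most nine countries: 2 × 9 = 18.
- Share of about 400 respondents: 18 / 400 = 4.5%. This is also the most by which they could move an overall proportion, in percentage points, if all 18 took part and each answered correctly only because of the pilot.
- In Sweden, Finland or Poland (target 5-10 HCPs each): 2/10 = 20% to 2/5 = 40% of the country sample, if both took part.

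**The case against.** The case against has several parts.

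- *The query sentence may concern only missing or practice fields.* It is conditional, an answered true/false item gives little to query, and data-handling detail is left to a data management plan that is not shown. This is plausible and keeps the point small. But the protocol sentence is unrestricted and sits beside a safeguard that it contradicts, and one clause would settle it.
- *Reminders are a deliberate response-rate measure.* This stands. A reader might infer from 9.6.1 that any recontact breaches 9.9, but 9.9 is not a general ban on contact.
- *Look-up is possible anyway.* This also stands. The survey is online, unsupervised and has no stated time limit, so a respondent can open the brochure in mid-session. Resumption adds to the risk and does not create it. Answers already saved stay locked under 9.4, and later pages may not have been seen before the break.
- *A single-session rule would be the natural cure.* A reader might want one, with no return after a break-off. Because only fully completed surveys are valid, break-offs would then be lost altogether. At a 4.4-6.8% response rate, that exchanges a bias of unknown size for a loss of respondents and possibly more selection. The documents do not support that trade.
- *The pilot point is minor.* No section says that pilot HCPs will be invited, and the 80% criteria are not set by country. Both are true, but their exclusion costs almost nothing and country-level results are planned.

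A reader might also want a number for the look-up bias. If true knowledge is p and a share f of those who would be wrong look up the answer, the observed rate is p + (1 − p)f, and 80% is reached at f = (0.80 − p)/(1 − p). That gives 33% at p = 0.70 (0.10/0.30), 20% at p = 0.75 (0.05/0.25) and 9% at p = 0.78 (0.02/0.22). Neither p nor f is in the protocol, nor is the share finishing in a later session. The result simply returns the assumption.

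**Conclusion.** The point holds in a limited form. The unrestricted query process in 9.6.1 conflicts with the safeguard in 9.9 wherever a scored item is concerned, and the lock point differs between 9.4 and 9.9. Separately, and without contradiction, resumption adds to a look-up risk that the survey already carries, and the plan does not mark the resumed surveys.

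The direction of any bias in the three 80% criteria is probably upward, assuming that queried or looked-up answers are more often correct than unaided ones. Its size cannot be derived from the document. The pilot overlap can be bounded: at most 18 of about 400, or 4.5% overall, assuming nine countries and that every pilot HCP is later surveyed. It matters mainly for countries with a target of 5-10. For the criteria specific to one HCP type, the 4.5% further assumes that pilot HCPs divide between prescribers and non-prescribers much as the sample does.

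**What to change.** 1. **Queries and lock point.** State in 9.6.1 that queries are limited to technical, screening and practice fields and never concern scored knowledge or behaviour items. Use one lock point, saved or submitted, in both 9.4 and 9.9.
2. **Resumption.** Keep reminders and the option to return. Record session times on the platform, flag respondents who completed the scored block in more than one session, and report the three 80% criteria with and without them.
3. **Pilot.** Add to the exclusion criteria in 9.2.2 any HCP who took part in the questionnaire pilot or user testing.

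The cost is a few sentences, a platform time stamp, one extra descriptive table and the loss of a few HCPs from the pool. The with/without table will not detect look-up within a single sitting, and the report should say so.
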